4.13 Safety Evaluation

All safety summaries and analyses will be based upon the SAF as defined in Section 4.4.1 unless otherwise specified in specific section.

All summaries will be provided by cohort and placebo across cohorts will be pooled.

In addition, the summary tables will be presented for by dose cohort, including pooled placebo, pooled active treatment across cohorts, pooled IV cohorts, pooled SC cohorts and overall.

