# 6.1. Study Interventions Administered

The study intervention composition and doses to be administered in this study are presented in Table 7.

Table 7: Dose Reference Chart for Study ALXN1910-HV-101

Study Intervention Name	ALXN1910 IV	ALXN1910 SC	Placebo
Туре	Biologic	Biologic	Placebo
Dose Formulation	ALXN1910 is formulated at pH 7.3 and each vial contains 100 mg of ALXN1910 in 10 mM sodium phosphate, 70 mM glycine, 210 mM sucrose, and 0.05% PS80.	ALXN1910 is formulated at pH 7.3 and each vial contains 100 mg of ALXN1910 in 10 mM sodium phosphate, 70 mM glycine, 210 mM sucrose, and 0.05% PS80	0.9% normal saline
Unit Dose Strength(s)/Dosage Level(s)	5 and 15 mg, single-dose	15, 45, and 135 mg, single-dose	0 mg, single-dose
Route of Administration	IV infusion	SC injection	IV infusion or SC injection
Use	Experimental	Experimental	Placebo
IMP and NIMP	IMP	IMP	IMP

Abbreviations: IMP = investigational medicinal product; IV = intravenous; NIMP = non-investigational medicinal product; PS80 = polysorbate 80; SC = subcutaneous

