# 9.4. Statistical Analyses

Statistical methods described in this section will be further elaborated in the SAP. This SAP will be developed and finalized before first data cutoff if interim analysis is conducted or database lock. Summary statistics will be computed and displayed by treatment group and by visit, where applicable. Participants in the placebo group of each cohort will be pooled in the analysis.

Descriptive statistics for continuous variables will minimally include the number of participants, mean, standard deviation, minimum, median, and maximum. For categorical variables, frequencies, and percentages will be presented. Graphical displays will be provided as appropriate.

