### 9.4.1. Safety Analyses

All safety analyses will be based on the Safety Set.

The primary objective of the study is to assess the safety and tolerability of ALXN1910. The endpoints to support the primary objective include incidence of TEAEs and TESAEs.

The incidence of TEAEs and TESAEs will be summarized by SOC and PT for each dose cohort overall, by intensity/severity, and by relationship to study intervention. Treatment-emergent AEs and TESAEs resulting in withdrawal from the study will be listed. Participants having multiple AEs within a category (eg, overall, SOC, PT) will be counted once in that category. For intensity/severity tables, a participant's most severe event within a category will be counted. Adverse events of special interest (such as ISRs and IARs) will be analyzed similarly.

Changes from baseline in vital signs and laboratory assessments (as displayed in Table 10) will be summarized by visit for each dose cohort and pooled placebo group. Laboratory parameter values will be assessed by the Investigator for intensity/severity grade by taking into consideration clinical judgment and using CTCAE version 5.0 (for grading see Section 10.3.3).

Shift tables by treatment group will be produced for these laboratory parameters. These tables will summarize the number of participants with each baseline intensity/severity grade relative to the normal ranges, and changes to the worst highest grade assessed postdose during the study

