3 INVESTIGATIONAL PLAN

3.1 Overall Study Design and Plan

This is a Phase 1, randomized, double-blind, placebo-controlled study designed to evaluate the safety, tolerability, PK, PD, and immunogenicity of SADs of ALXN1910 SC and a SAD of ALXN1910 IV in up to approximately 48 healthy adult participants across treatment cohorts (up to approximately 36 participants to receive ALXN1910 and up to approximately 12 participants to receive placebo) (Table 1). Of the 48 participants, 8 will be of Japanese descent, defined as those participants whose parents and grandparents are both Japanese and who have spent less than 10 years outside of Japan.

Cohortª	Number of Participants (ALXN1910:Placebo)	Route of Administration	Dose	Number of Doses/Dose Interval
1	8 (3:1)	IV ^b	5 mg	Single dose
2	8 (3:1)	SC	15 mg	Single dose
3	8 (3:1)	IV ^b	15 mg	Single dose
4	8 (3:1) (Japanese participants)	SC	15 mg	Single dose
5	8 (3:1)	SC	45 mg	Single dose
6	8 (3:1)	SC	135 mg	Single dose

 Table 1
 Planned ALXN1910-HV-101 Dosing Cohorts

^a Cohort 3, Cohort 4, and Cohort 5 can be initiated in parallel after dose escalation decision following SRC review of Cohort 2 safety and PK data.

^b Slow IV infusions (rate of infusion = 6 mL/h) using a controllable infusion pump. The pharmacy manual will include details regarding infusion rate and duration.

Abbreviations: IV = intravenous; PK =pharmacokinetic; SC = subcutaneous; SRC = Safety Review Committee

[figure not shown]
For this FIH study, 8 participants will be randomly assigned in a 3:1 ratio to treatment and placebo in each of the 6 cohorts with escalating doses of 5 mg IV (Cohort 1), 15 mg SC (Cohort 2), 15 mg IV (Cohort 3) in parallel with 15 mg SC in Japanese participants (Cohort 4) and 45 mg SC (Cohort 5), followed by 135 mg SC (Cohort 6). The first 2 participants randomized to each cohort will be dosed as a sentinel pair, with 1 participant on active treatment and 1 participant on placebo. This dosing strategy is justified given the large exposure margins (approximately 15-fold at the highest planned single dose of 135 mg SC).

Participants who meet the qualifications for the study based on screening will be admitted to the CRU the day prior to dosing (Day -1) to undergo Check-in assessments per the applicable SoA (Section 6.1).

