Relationship (Causality)

TEAEs will be summarized by SOC, PT, and causality, including the number and percentage of participants experiencing events. Relationship to study drug will be tabulated respectively. If a participant reports the same TEAE more than once within that SOC and PT, the TEAE with the

strongest relationship to study drug will be counted. In summaries including relationship to study treatment, the following relationships will be summarized: 'Not related', 'Related'. Participants who experience the same event multiple times will be included in the most related category. Events with missing relationship will be considered as 'Related' to the last given study drug for summary purposes but recorded as missing in the listings.

Adverse Events of Special Interest (AESI)

Adverse events of special interest (AESI) will be summarized by SOC and PT, including the number and percentage of participants experiencing events. Listing of AESI will be provided.

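### Injection and infusion reaction tables show IV and SC columns beside one mixed-route placebo column; adding placebo by route would give a matched reference

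*SAP*

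**What the plan says.** The pooling rule has no exception by route or type of event. SAP 4.13 says of the safety summaries: "All summaries will be provided by cohort and placebo across cohorts will be pooled". Protocol 9.4 says: "Participants in the placebo group of each cohort will be pooled in the analysis". SAP 4.13 then lists the table columns as dose cohorts, "including pooled placebo, pooled active treatment across cohorts, pooled IV cohorts, pooled SC cohorts and overall". Route is thus separated for the cohorts, while placebo has one column.

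Placebo is saline, and Protocol Table 7 (Section 6.1) gives its route as "IV infusion or SC injection". Cohorts 1 and 3 are IV; Cohorts 2, 4, 5 and 6 are SC.

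For the reactions themselves, Protocol 9.4.1 says "Adverse events of special interest (such as ISRs and IARs) will be analyzed similarly", meaning in the same way as other treatment-emergent events. SAP 4.13.1 says "Adverse events of special interest (AESI) will be summarized by SOC and PT, including the number and percentage of participants experiencing events", and adds a listing. The SAP does not define the special-interest events, so the link to ISRs and IARs comes from the protocol. SAP 4.17 plans no subgroup analysis, so a route-specific placebo summary does not appear elsewhere.

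**The concern.** Pooling placebo over cohorts is sensible in a small ascending-dose study when an event has little to do with how the dose was given. ISRs and IARs are different, because they are tied to the administration. A needle in subcutaneous tissue and an infusion into a vein can each produce a reaction with saline alone, and not necessarily at the same rate. Protocol Table 4 itself treats site reactions as a risk of any agent given by either route.

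The placebo participants supply the background rate for the procedure. If that background differs by route, the mixed column is the right reference for neither the SC nor the IV cohorts. What is at stake is how the study report reads on the first risk in Table 4, under a primary objective of safety and tolerability that rests entirely on descriptive tables.

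**Working it through.** **Background check.** The plan's only figures of this kind are the probabilities of seeing at least one event among 6 active participants (Protocol 9.2, SAP 3.2). The formula 1 - (1 - p)^6 gives 46.9%, 62.3%, 73.8%, 82.2%, 88.2%, 92.5% and 95.3% at p = 10% to 40% in steps of 5 points. All seven agree with the table. They do not bear on the placebo column.

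**Composition of the placebo column.** Eight participants per cohort at 3:1 gives 6 active and 2 placebo (SAP 3.1, Table 1).

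| Route | Cohorts | Active | Placebo |
|---|---|---|---|
| IV | 1, 3 | 2 x 6 = 12 | 2 x 2 = 4 |
| SC | 2, 4, 5, 6 | 4 x 6 = 24 | 4 x 2 = 8 |
| All | 1 to 6 | 36 | 12 |

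The totals match the 36 and 12 in SAP 3.1. Pooled placebo is one third IV and two thirds SC. The SAP does not say whether its pooled IV and pooled SC columns contain active participants only (12 and 24) or everyone in those cohorts (16 and 32). Under either reading there is no placebo column for one route.

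**Size of the shift.** Let p_IV and p_SC be the placebo reaction rates and D = p_SC - p_IV.

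- Pooled placebo rate = (4 p_IV + 8 p_SC)/12.
- Shift in the SC active-minus-placebo difference when pooled placebo replaces SC placebo = p_SC - pooled = 4D/12 = D/3.
- Shift in the IV difference = p_IV - pooled = -8D/12 = -2D/3.

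The active rate cancels, so the shift depends only on D. When D is not zero, the IV shift is always twice the SC shift, in the opposite direction.

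**Range.** The documents give no placebo reaction rate by route. The rates below are assumptions.

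| Assumed IV placebo | Assumed SC placebo | Pooled | SC shift (points) | IV shift (points) |
|---|---|---|---|---|
| 0% | 10% | 6.7% | +3.3 | -6.7 |
| 5% | 20% | 15.0% | +5.0 | -10.0 |
| 0% | 25% | 16.7% | +8.3 | -16.7 |
| 10% | 40% | 30.0% | +10.0 | -20.0 |
| 25% | 5% | 11.7% | -6.7 | +13.3 |
| 20% | 20% | 20.0% | 0 | 0 |

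**Precision lost by splitting.** With no events, the exact two-sided 95% upper limit is 1 - 0.025^(1/n): 26.5% at n = 12, 36.9% at n = 8 and 60.2% at n = 4.

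**The case against.** The strongest reply is that nothing in the plan formally uses the mixed rate. Protocol 9.1 tests no hypotheses, and no active-minus-placebo difference or interval is planned for adverse events. The ISR and IAR stopping rules in Protocol Table 11 are counts of affected participants with no placebo reference. Escalation rests on the Safety Review Committee's review (Protocol 6.6 and 9.6). All of this stands, and it confines the point to how a table is read.

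A reader might infer that pooling necessarily makes the drug look worse by one route and better by the other. The documents do not support that. It depends on D, for which they give no value: equal rates give no shift, and a higher IV rate reverses it. Nor do they show that every IAR, which includes hypersensitivity, differs by route after saline. At the planned numbers, the 0%/25% row amounts to two reactions among 8 SC placebo participants.

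The information is also not lost. SAP 4.8.1 lists each participant's route and SAP 4.13.1 lists the special-interest events, so 12 placebo participants can be sorted by hand. That is true, but no summary table does it.

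Finally, the split groups are very small, and one event moves a group of 4 by 25 points. The IV group is not uniform either: SAP 3.3.2 gives nominal infusion times of within 5 seconds for Cohort 1 and 0.5 hours for Cohort 3. This is a good argument against replacing pooled placebo with the split. It is not an argument against showing both.

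Column layout may be settled in the table shells, which are not among these documents. The SAP's mention of shells in 4.13.1 concerns the analysis set and does not indicate a route split.

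**Conclusion.** The point holds as a matter of presentation. The ISR and IAR tables offer one placebo column, planned as 4 IV and 8 SC, beside separate IV and SC columns, and neither document provides a route-matched placebo summary. Reading those tables against pooled placebo shifts the SC excess by D/3 and the IV excess by -2D/3. Over the assumed rates above, this runs from nothing to 10 points for SC and 20 points for IV, in either direction.

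The result assumes that cohorts fill as planned at 6 active and 2 placebo, and that placebo follows the cohort's route. A reader might go further and infer a biased comparison or a compromised safety decision. The plan contains no such formal comparison, and no decision rule uses the placebo rate. The SAP also follows the protocol here, so there is no inconsistency between them to resolve. This is an inexpensive improvement to descriptive tables that serve the primary objective.

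**What to change.** In SAP 4.13.1, for the special-interest (ISR and IAR) summary tables only, add an IV-placebo column (planned n = 4) and an SC-placebo column (planned n = 8), each next to the active columns of the same route. Keep the pooled placebo column in those tables and in every other safety table. State that the route-specific columns are to be read mainly as counts. This fits SAP 4.2.6, under which report text gives frequencies only when samples are small. The same edit should say whether the pooled IV and pooled SC columns exclude placebo, so that the matching active column is clear.

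The cost is two columns in a few tables, with no new data and no change to the design. The downside is imprecision: a zero in the IV-placebo column is still compatible with a true rate of up to 60.2%, and in the SC-placebo column up to 36.9%, against 26.5% for pooled placebo. Keeping the pooled column lets the reader weigh the larger mixed group against the smaller matched ones.

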4.13.1 Adverse Events

All outputs for AEs/treatment-emergent adverse events (TEAEs) will be based on the SAF unless specified separately in TLF shells. AEs will be coded using the Medical Dictionary for Regulatory Activities (MedDRA®), version 24.1 or latest.

All AE summaries should provide the number and percentages of participants reporting at least one AE and the total number of events reported.

Summaries of AEs will include the following:

- Incidence of TEAEs (by dose and by cohort and overall, SOC, and PT)
- Incidence of TEAEs by highest relationship (by cohort and overall, SOC, and PT)
- Incidence of TEAEs by worst severity (mild/moderate/severe/life threatening/fatal, by cohort and overall, SOC, and PT)

Summary tables will contain counts of participants, percentages of participants in parentheses, and the number of events where applicable. A participant who has multiple events in the same SOC and PT will be counted only once in the participant counts, but all events will be included.

All Adverse Events (AEs)

All AEs will be listed including pretreatment AEs.

Treatment-emergent Adverse Event (TEAE)

A TEAE will be defined as any AE that emerges during treatment (i.e., an AE that started after study drug administration or pre-existed that worsened in severity after study drug administration) and will be analyzed for the purpose of safety analysis.

TEAEs will be summarized by SOC and PT, including the number and percentage of participants experiencing events, separately.

A by-participant listing of all TEAEs leading to withdrawal from the study will be provided.

Severity

TEAEs will be summarized by SOC, PT, and severity, including the number and percentage of participants experiencing events. If a participant reports the same TEAE more than once within that SOC and PT, the TEAE with the highest severity will be used in the corresponding severity summaries.

In summaries including severity, the following intensity categories will be summarized as per CTCAE version 5.0 published 27 Nov 2017: 'Mild', 'Moderate', 'Severe', 'Life-threatening', 'Fatal'. Participants who experience the same event multiple times will be included in the most severe category. Events with missing intensity will be considered as 'Severe' events for summary purposes but recorded as missing in the listings.

If severity is reported by Common Terminology Criteria for Adverse Events (CTCAE) grade, then summary of severity will be presented using CTCAE grade.

Relationship (Causality)

TEAEs will be summarized by SOC, PT, and causality, including the number and percentage of participants experiencing events. Relationship to study drug will be tabulated respectively. If a participant reports the same TEAE more than once within that SOC and PT, the TEAE with the

strongest relationship to study drug will be counted. In summaries including relationship to study treatment, the following relationships will be summarized: 'Not related', 'Related'. Participants who experience the same event multiple times will be included in the most related category. Events with missing relationship will be considered as 'Related' to the last given study drug for summary purposes but recorded as missing in the listings.

Adverse Events of Special Interest (AESI)

Adverse events of special interest (AESI) will be summarized by SOC and PT, including the number and percentage of participants experiencing events. Listing of AESI will be provided.

4.13.2 Deaths, Serious Adverse Events, and Other Significant Adverse Events

A by-participant listing of all serious adverse events will be created. These may include the following listings:

• A by-participant listing of all TESAEs leading to withdrawal from the study

Listings should follow the format described for AEs in Section 4.13.1 if appropriate.

Statistical Analysis Plan

4.13.4 Vital Signs

A by-participant listing of all vital sign measurements (including weight) and change from baseline will be presented.

This listing will include a flag for measurements identified as treatment-emergent markedly abnormal (TEMA)/potentially clinically significant (PCS) as calculated by the criteria outlined in Table 4.

Measured (observed) values including changes from baseline will be summarized by cohort and time point and by vital sign parameter (Oral temperature, pulse rate, respiratory rate, and systolic and diastolic blood pressure (mm Hg)).

Measurements obtained at Screening will not be included in the shift tables or in the tabulations of descriptive statistics.

Statistical Analysis Plan

Measurements obtained prior to dosing will be included in the tabulations for the treatment received in that specific treatment cohort.

Table 4 TEMA/PCS Criteria for Vital Signs

Variable	Unit	Criterion		
, and a set of the set	C III	Low	High	
Systolic blood pressure	mmHg	≤ 80 mmHg and ≥ 20 mmHg decrease from Baseline	≥ 140 mmHg and ≥ 20 mmHg increase from Baseline	
Diastolic blood pressure	mmHg	Value ≤ 60 and ≥ 15 decrease from Baseline	Value ≥ 90 and ≥ 15 increase from Baseline	
Pulse rate	bpm	Value ≤ 40 and ≥ 15 decrease from Baseline	Value ≥90 and ≥15 increase from Baseline	

Note: The change in measurement (increase or decrease) will be calculated relative to the value obtained at baseline.

Both conditions must be satisfied for a measurement to be considered potentially clinically significant; bpm = Beats per minute.

Box plot of vital sign parameters over time will be presented for systolic BP, diastolic BP, and pulse rate.

4.13.5 ECG

Standard safety 12-lead ECGs will be performed as shown in the Section 6.1.

The following ECG parameters will be recorded:

Heart rate (HR) (beats per minute [bpm]) PR interval (msec) QRS interval (msec) QT interval (msec) QTc interval (msec)

QTcF interval (msec)

The ECG will be evaluated by the Investigator as 'Normal', 'Abnormal, NCS' or 'Abnormal, CS'.

All ECG parameters will be listed by participant including changes from baseline by dose cohort, including pooled placebo, pooled active treatment across cohorts, pooled IV cohorts, pooled SC cohorts and overall.

Baseline is defined in Section 4.2.4.

Descriptive statistics for absolute values and changes from baseline will be presented by cohort. A categorical QTc analysis will also be performed.

Measurements obtained at Screening will not be included in the shift tables.

A summary of the number and percentage of participants with the following QT/QTc intervals of ECG parameters will be displayed in a frequency table at each visit by dose cohort, including pooled placebo, pooled active treatment across cohorts, pooled IV cohorts, pooled SC cohorts and overall cohort:

ALXN1910-HV-101

Statistical Analysis Plan

- QT, QTcF interval ≤ 450 msec
- 450 msec < QT, QTcF interval \leq 480 msec
- 480 msec < QT, QTcF interval \leq 500 msec
- QT, QTcF interval > 500 msec
- QT, QTcF interval increases from baseline ≤ 30 msec
- 30 msec < QT, QTcF interval increases from baseline ≤ 60 msec
- QT, QTcF interval increases from baseline > 60 msec

The listing of ECG abnormality will be presented separately.

Mean of the triplicates for ECG measurements will also be presented in the listing and used for deriving baseline and change from baseline.

4.13.6 12-Lead Holter ECG

Not applicable.

4.13.7 Physical Examination

Physical examinations will be performed as shown in the Section 6.1.

The full physical examination includes an assessment of general appearance and a review of systems (dermatologic, head, eyes, ears, nose, mouth/throat/neck, thyroid, lymph nodes, respiratory, cardiovascular, gastrointestinal, extremities, musculoskeletal, neurologic systems).

The brief physical examination includes an assessment of the general appearance, skin, abdomen, cardiovascular system and lungs.

Clinically significant physical examination findings will be listed.

4.13.8 Daylight Saving Time (DST):

DST is not implemented at clinbase level, hence not applicable.

4.13.9 Safety Monitoring (Safety Review Committee)

The blinded SRC, consisting of the Investigator, Medical Monitor, Drug Safety Physician, Study Statistician, and Clinical Pharmacologist will evaluate the available study data at prespecified time points for participant safety and make recommendations on dose escalation, dose modification, or termination of the study. Decisions to continue, modify (explore the dose cohort further), or escalate dosing will be made by the Investigator and/or SRC.

The SRC will meet at minimum to support each cohort dose escalation after review of blinded data. Where review of unblinded data may be necessary in the event of emerging safety signals, additional ad hoc meetings will be scheduled without the Investigator/site staff in attendance. If dosing is stopped because of a safety event, continuation of the cohort and/or study will require a substantial amendment.

